3.7.1.4 Healthcare Utilization Record Evaluation (Month -6 Through Month 6/ET)

Healthcare utilization record evaluation will take place 6 months prior to and following the baseline (Day 1) visit (for a total of 12 months) to evaluate the subject health records and to examine subject interaction with the investigators prior to and following usage of Abilify MyCite. All hospital admissions and number of days spent in an inpatient setting (psychiatric) would be recorded and assessed as either ‘planned’ or ‘unplanned’ and ‘related’ or ‘unrelated’ to the psychiatric illness. Similarly, all encounters between any investigators (psychiatric) and the subject will be recorded to obtain the following information:

- The nature of the contact (eg, office visit, partial hospitalization).
- The investigator role (eg, community psychiatric nurse).
- Whether the contact was planned or not.
- Whether or not the contact was initiated as a result of data from Abilify MyCite.
- Any medication titration, adherence counseling, education, and lifestyle coaching.

Intervention data includes psychiatric hospitalizations, outpatient visits, the number of crisis interventions, and pharmacy cost of all medications. This data will be recorded in the eCRF at Month 3 and Month 6/ET.

Protocol 031-201-00301

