7.1.2 Technical Details

Inpatient psychiatric hospitalization is defined as closed (locked) ward or open ward inpatient psychiatric hospitalization, where the hospitalization is not primarily for psychosocial reasons.

The start date and end date of the retrospective period Months 1-3 are calculated in the following ways: start date = (Date signing informed consent - 28*6 Days) and end date = (Date of signing informed consent - 28*3-1 Days). The start date and end date of the prospective period Months are calculated as: start date = (Mycite start date) and end date = (Mycite start date + 28*3 - 1). Similarly, the start date and end date of the retrospective period Months 4-6 are calculated in the following ways: start date = (Date signing informed consent - 28*3 Days) and end date = (Date of signing informed consent -1 Days). The start date and end date of the prospective period Months are calculated as: start date = (Mycite start date + 28*3) and end date = (Mycite start date + 28*6 - 1).

Inpatient psychiatric hospitalization is deemed to occur during the retrospective (or prospective) Months 1-3 if:

- The hospitalization starts before the start date of retrospective (or prospective) Months 1-3 and continues into Months 1-3
- The hospitalization starts during the retrospective (or prospective) period.

Similarly, Inpatient psychiatric hospitalization is deemed to occur during the retrospective (or prospective) Months 4-6 if:

- The hospitalization starts before the start date of retrospective (or prospective) Months 4-6 and continues into Months 4-6
- The hospitalization starts during the retrospective (or prospective) period

All the above hospitalization in Months 1-3 and Months 4-6 will be counted in the Month 1-6 period.

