Psychiatric partial hospitalization program, psychiatric intensive outpatient program or psychiatric assertive community treatment program are reported in their corresponding category in the CRF panel of psychiatric non-inpatient treatment visits. For each category of the program, number of programs during the 3 months (Months 1-3) of the retrospective (or prospective) period can be determined by their number of occurrences during the respective period. Duration (i.e., the total number of stays/sessions) of each program is derived as the product of the mean number of stays/sessions attended per week (as recorded in CRF) and the overall length of the program in weeks, rounded to the smallest following integer. For both retrospective and prospective periods, the overall length of each program defined as $\min(\text{Program End Date, End date of the 3 months of}$

Protocol 31-201-301 Interim Analysis Plan

the respective period) – max(Program Start Date, Start date of the 3-months of the respective period) + 1. For each subject, cumulative duration for each category of the programs is the sum of duration of each program in that category and mean duration is the average over all reported programs in that category.

Number of psychiatric emergency visit, psychiatric outpatient treatment visit, nonpsychiatric emergency room visit, nonpsychiatric urgent care facility visit, or nonpsychiatric outpatient visit can be determined from their reported occurrences in the category of emergency room and/or outpatient treatment visits from CRF. Psychiatric outpatient treatment visit will include such visits with a psychiatrist (MD) provided in a private doctor’s office, with a psychiatrist (MD) provided in a hospital outpatient clinic, or of other type. Nonpsychiatric outpatient visit will include such visits with a medical doctor provided in a private doctor’s office, with a medical doctor provided in a hospital outpatient clinic, or of other type.

For endpoints in the form of change from baseline, baseline definitions are provided in [Section 5.1.2](#).

[Redacted content]

Protocol 31-201-301 Interim Analysis Plan

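### SAP 7.4.1.2 gives program length in weeks in one sentence and computes it in days in the next; taken literally, session totals come out up to about 7 times too high

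*SAP*

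**What the plan says.** SAP 7.4.1.2 builds the duration of a non-inpatient program in two steps.

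- The product: "Duration (i.e., the total number of stays/sessions) of each program is derived as the product of the mean number of stays/sessions attended per week" (a CRF item) and "the overall length of the program in weeks, rounded to the smallest following integer".
- The length: "For both retrospective and prospective periods, the overall length of each program defined as" the earlier of the program end and the period end, minus "max(Program Start Date, Start date of the 3-months of the respective period) + 1".

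Cumulative duration then sums over programs in a category, and mean duration averages over them. SAP 7.4.1.1 summarizes these quantities descriptively and compares the retrospective and prospective periods by paired t-test.

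On visit counts, the same section says that psychiatric emergency and outpatient visits "can be determined from their reported occurrences in the category of emergency room and/or outpatient treatment visits from CRF". Outpatient visits include those "with a psychiatrist (MD) provided in a hospital outpatient clinic, or of other type". Protocol 3.7.1.4 says that "all encounters between any investigators (psychiatric) and the subject will be recorded to obtain the following information", and the items listed include whether a contact was planned and whether MyCite data prompted it.

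**The concern.** A rate per week has to be multiplied by a number of weeks. The first sentence names that unit, but the only formula supplied returns days. The same end-minus-start-plus-1 form appears earlier in SAP 7.4.1.2 for inpatient stays, where days are the right unit, so a programmer could easily carry it over unchanged. The rounding instruction does not resolve the conflict. A day count is already an integer, and the sentence does not say whether the weeks or the product is rounded.

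At stake are the published session totals per subject, their means, and the retrospective-to-prospective difference. These bear on the expectation in Protocol 2.1 that MyCite use will lower overall healthcare utilization.

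A smaller question concerns visit counts. Trial visits exist only in the prospective period. If sites enter them as psychiatric outpatient visits, prospective utilization rises for a reason unrelated to treatment effect.

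**Working it through.** The plan gives no numeric result for this derivation, so there is no figure to reproduce. The check is on units, followed by direct arithmetic.

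**Period length (SAP 7.1.2).** The prospective Months 1-3 period starts on the MyCite start date and has "end date = (Mycite start date + 28*3 - 1"), so it lasts 83 - 0 + 1 = 84 days, or 12 weeks. The retrospective Months 1-3 period runs from consent - 168 to consent - 85, so it lasts -85 + 168 + 1 = 84 days as well.

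**Three readings.** Let r be sessions per week and d the day count from the length formula. The rates and lengths below are illustrative.

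- A: round the product up, ceil(r × d/7)
- B: round the weeks up, r × ceil(d/7)
- C: put the day count straight into the product, r × d

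| r | d | A | B | C | C/A | C/B |
|---|---|---|---|---|---|---|
| 3 | 84 | 36 | 36 | 252 | 7.0 | 7.0 |
| 3 | 42 | 18 | 18 | 126 | 7.0 | 7.0 |
| 3 | 30 | 13 | 15 | 90 | 6.9 | 6.0 |
| 3 | 10 | 5 | 6 | 30 | 6.0 | 5.0 |
| 1 | 1 | 1 | 1 | 1 | 1.0 | 1.0 |

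Steps for the third row: 30/7 = 4.29 weeks. Under A, 3 × 4.29 = 12.86, which rounds up to 13. Under B, 4.29 rounds up to 5, and 3 × 5 = 15. Under C, 3 × 30 = 90.

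Whole-week programs give a ratio of exactly 7. Other lengths of 5 days or more give mostly 5 to 7. Very low rates over short spans can fall below that: 0.5 per week over 5 days gives 1 under A and 3 under C (2.5 rounded up), a ratio of 3. One-day programs can show no inflation.

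**Effect on the test.** The paired statistic is t = mean(D)/(SD(D)/√n). If every difference D is multiplied by 7, the numerator and the denominator both grow 7-fold and t is unchanged. Rounding makes the scaling inexact, so t is nearly rather than exactly the same. The mean difference itself is reported about 7 times too large.

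**Scheduled visits.** Protocol 3.1 sets investigator evaluations at Day 1, Month 3 and Month 6/ET, and dispensing visits at Months 1, 2, 4 and 5. With a 28-day schedule and the -3/+2 day window, the visits that can fall within prospective Days 1-84 are Day 1, Month 1, Month 2, and Month 3 when it occurs by Day 84.

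- None entered as outpatient treatment visits: 0 added
- Investigator evaluations only: 1 to 2 added
- All visits entered: 3 to 4 added

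The retrospective window closes before consent, so its matching count is 0.

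**The case against.** The strongest reply is that the SAP does state the unit. A reader might infer that the plan prescribes totals 7 times too high. It does not: the words in weeks stand in the sentence that defines the product, and a programmer who honours them gets 36 sessions, not 252. The inflation is conditional on literal use of the length formula, and the factor is not uniformly 7. This stands, and it limits the claim. It does not remove the defect, because the only explicit formula for the length returns the wrong unit.

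It is also fair to say that inference would hardly change, since the same formula applies in both periods, and that these are exploratory variables. Both points stand. The descriptive means and differences would still be wrong.

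A reader might also infer that scheduled trial visits are counted as prospective utilization. The documents do not say so. Protocol 3.7.1.4 gives a community psychiatric nurse as an example role and covers six months before baseline, which points to care-provider contacts generally. The SAP's residual outpatient category does not tell sites to enter study visits. The months with dispensing visits need not involve psychiatric treatment at all. Any extra contacts would count against MyCite rather than create a benefit. Parts of this SAP section and the exploratory endpoints are redacted, so a counting rule may exist out of sight. The planned/unplanned item would not by itself separate trial visits from routine appointments, since both are planned. What remains is a request for clarification.

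**Conclusion.** The unit conflict in SAP 7.4.1.2 is real and should be corrected. If the length formula is coded as written, session totals and reported paired differences are 7 times too large for whole-week programs and mostly about 5 to 7 times too large for other lengths of 5 days or more. If the stated unit is applied, there is no error, and only the rounding ambiguity is left (13 or 15 sessions for 3 per week over 30 days). The paired t statistic is nearly unchanged in either case. The primary endpoint (inpatient psychiatric hospitalization, McNemar test) and the secondary endpoint (PDC) do not use this derivation.

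The handling of scheduled visits is an open question, not a demonstrated error. Its possible size is 0 to 4 added contacts per subject in prospective Months 1-3, and the figure depends on site entry practice that the visible documents do not describe.

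**What to change.** In SAP 7.4.1.2:

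1. Define length in weeks as (min(program end, period end) - max(program start, period start) + 1)/7.
2. Multiply by mean sessions per week and round the product up to the next integer, stating that the product, not the number of weeks, is rounded.
3. As a clarification, state that contacts on scheduled-visit dates made only for the trial are excluded from the utilization counts, while unscheduled and MyCite-triggered contacts are kept.

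The first two items cost one corrected formula and one clause. The third costs one SAP sentence and a match of encounter dates to scheduled-visit dates. No change to the design, the sample size or the primary analysis is needed. A simple output check would guard the derivation: 252 sessions in 84 days would mean 252/84 = 3 sessions a day, which cannot be squared with a recorded rate of 3 a week.

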7.4.2 Other Analyses

The dashboard data is collected every 2 weeks by physicians or caregivers. The summary statistics of dashboard access by month, at Month 3, and Month 6 will be provided. The features on decision/discussion making will be summarized by the following categories: pill ingestion data, Subject reported reason code for missed doses, missed dose alert, activity, rest, mood, and subject reported rest quality rating. The count and percentage of general medical/treatment decisions made as a result of MyCite data will be summarized as: no change to treatment, adherence counseling, provided patient education, recommendations on lifestyle changes, medication changes, referred to other service/specialist, other. Further the subgroup of medication changes (increase dose, decrease dose, added medication, stopped medication, alter medication) will also be summarized.

8 Safety Analyses

In general, safety variables will be summarized by incidence and listed for Safety Samples.

Safety variables to be analyzed include AEs, clinical laboratory tests, vital signs, ECGs, physical examination findings, weight, height, BMI, extrapyramidal symptoms (EPS), suicidality using the C-SSRS, investigator rating of injection site reaction, subject reported visual analogue scale (VAS) score of injection site pain.

In general, summary statistics of changes from baseline will be provided for safety variables based on all available data for each post-baseline visit and for the last visit as well. Baseline and last visit measurements of safety variables are defined as in [Section 5.1.2](#). Data from the unscheduled visits are included in the mean change from baseline calculation and in the incidence's calculation.

8.1.1 Adverse Events

All adverse events (AEs) are coded by system organ class and Medical Dictionary for Regulatory Activities (MedDRA version xx) preferred term. A treatment-emergent AE (TEAE) is defined as an AE which starts after start of study medication (MyCite), or an AE continues from baseline and is serious, study drug-related, or results in death,

discontinuation, interruption or reduction of study medication. If the AE increases severity or frequency during this study, a new AE should be recorded.

Adverse events will be analysis by the following groups:

- TEAEs by severity

Protocol 31-201-301 Interim Analysis Plan

- Potentially drug-related TEAEs
- TEAEs with an outcome of death
- Serious TEAEs
- Discontinuations due to TEAEs
- TEAEs with at least 2% incidence
- TEAEs with at least 5% incidence

In addition, deaths, SAEs, and AEs leading to discontinuation from study or study treatment will be listed.

For the purpose of this trial, device-related SAEs include any event that is related to the IEM, patch, or the phone and app (reported to Otsuka). Device-related AE/SAE will be summarized. If an AE is related to the patch, then the skin irritation scoring system will be completed by the investigator. Patch-related AEs Grade 2 or above will be considered medically significant for purposes of this trial. Scores from the skin irritation will be summarized by irrigation grade.

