3.1 Type/Design of Trial

This is a phase 3b, open-label, prospective, clinical trial designed to assess the difference between inpatient psychiatric hospitalization rates in subjects on oral standard-of-care antipsychotic treatment(s) for a period of 6 months followed by a switch to Abilify MyCite for a period of 3 months (Months 1 to 3). At the Month 3 visit, the investigator should decide if subjects will continue on Abilify MyCite for an additional 3 months (Months 4 to 6) or switch to a standard-of-care treatment (eg, oral atypical antipsychotics or a long acting injectable [LAI]) for the duration of treatment.

Protocol 031-201-00301

This trial will include male and female subjects who are 18 to 65 years of age, inclusive, with a diagnosis of schizophrenia according to Diagnostic and Statistical Manual of Mental Disorders, Fifth Edition (DSM-5) criteria. Subjects must have had at least 1 inpatient psychiatric hospitalization within 4 years (48 months) and must have been prescribed oral antipsychotics for at least 6 months or longer prior to screening.

Subjects will enter a screening period (up to 45 days). If deemed eligible to participate, subjects will enter an open-label Abilify MyCite treatment prospective phase for up to 6 months.

Oral Standard-of-Care Antipsychotic Treatment(s) (Retrospective Phase)

To be eligible for trial participation, subjects must have been prescribed oral antipsychotic standard-of-care pharmacotherapy for at least 6 months or longer, with evidence of prescription (ie, pharmacy records) during the retrospective phase and prior to screening. Subjects administered antipsychotics other than aripiprazole must cross-titrate onto oral aripiprazole during the screening period at the discretion of the investigator to be eligible for trial participation.

Screening

After providing informed consent, subjects will enter the 45-day (Days -45 to -1; approximately 6 weeks) screening period to determine if they are eligible to enter the Abilify MyCite treatment (prospective) phase. The subject's past psychiatric history for the 6 months prior to screening must be available, inclusive of a comprehensive review of all psychiatric hospitalizations and interventions (psychiatric only).

As safety of the subject dictates, 2 options are available to the investigator as subjects transition from the screening period to the Abilify MyCite treatment (prospective) phase:

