Subjects will be monitored on the technology by the investigators, who can review the physician dashboard data and make changes to current treatment plan and therapy at their discretion. The investigators may request that a subject return to the site for unscheduled visits as deemed appropriate. In the event of an unscheduled visit, data collected will be at the investigator discretion per allowed data collection points noted in the schedule of assessments (Table 3.7-1). By Day 14 of the trial, if it is the opinion of the investigator that it is not appropriate for a subject to continue using Abilify MyCite, then the subject may be discontinued from trial participation but will be followed on oral atypical antipsychotic medication through the Month 6/ET visit.

Subjects will also visit the clinic for dispensing patches, Abilify MyCite product, and other supplies at Months 1, 2, 4, and 5. Any treatment changes, including reason for the change, will be recorded in the eCRF. Additionally, clinical evaluations will occur at Month 3 visit.

At the Month 6/ET visit, designated assessments and procedures will be conducted. The Month 6/ET visit marks the end of the assessment period. The subject will stop taking

Protocol 031-201-00301

Abilify MyCite product and will restart his/her standard-of-care treatment (routine follow-up from care teams). All trial materials will be returned to the trial site.

For subjects continuing on Abilify MyCite, a follow-up telephone contact will be made 30 days (\pm 3 days) after the last dose of aripiprazole tablet embedded with an IEM sensor (Abilify MyCite) product (for subjects who withdraw early and for those who complete the trial). The Month 6/ET visit will serve as the final safety visit for subjects who complete the study on standard-of-care treatment.

Trial assessment time points are summarized in [Table 3.7-1](#).

Protocol 031-201-00301

Table 3.7-1 Schedule of Assessments										
Assessments	Screening Days -45 to -1	Prospective Phase (Day 1 to Month 6/ET)^a							Follow -Up^b	Notes
		Abilify MyCite treatment required (Months 1 to 3)			Abilify MyCite or PRN oral atypical antipsychotic treatment (Months 4 to 6)					
		Baseline	Month 1	Month 2	Month 3	Month 4	Month 5	Month 6/ET	Month 7	
		Day 1	- 3/+ 2 days			- 3/+ 2 days			± 3 days	
Record retrospective hospitalization and intervention data per protocol	X ^c									
Informed consent	X									Section 3.4.1
Inclusion/exclusion criteria	X									Section 3.4

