3.7.1.3.5 Month 6/Early Termination Visit

Month 6/ET (- 3/ + 2 days) will be an investigator visit for the subject. In addition, Month 6/ET visit evaluations are to be completed for any subject withdrawn from the trial at any time (for any reason other than full withdrawal of the consent). At the Month 6/ET visit, the following will be performed:

- Administer the suicidality assessment (C-SSRS Since Last Visit Version; [Section 3.7.3.5](#)).
- Perform vital signs assessment ([Section 3.7.3.3](#)).
- Monitor AEs, including device-related nonserious AEs ([Section 5](#)).
- Accountability of patches and Abilify MyCite product (aripiprazole tablet embedded with an IEM sensor) supplies performed for subjects remaining on Abilify MyCite treatment. Any treatment changes, including reason for the change, will be recorded in the eCRF.
- Review Abilify MyCite dashboard data every 2 weeks for subjects remaining on Abilify MyCite treatment.

Protocol 031-201-00301

- [REDACTED]
- [REDACTED]
- [REDACTED]
- [REDACTED]
- [REDACTED]
- [REDACTED]
- Healthcare utilization record evaluation ([Section 3.7.1.4](#)).
- [REDACTED]
- [REDACTED]
- [REDACTED]
- [REDACTED]

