3.8.3 Individual Subject Discontinuation

3.8.3.1 Treatment Discontinuation

After enrollment, a subject may stop Abilify MyCite treatment permanently for a variety of reasons. Treatment discontinuations may be initiated by a subject who is not satisfied with treatment or may become medically necessary due to AEs, device-related nonserious AEs, required treatment with a disallowed medication or therapy, or other issues, as determined by the investigator. For subjects who elect to discontinue early for any reason, the sponsor would like to follow the subject for the total trial duration to track healthcare utilization with and without use of Abilify MyCite.

By Day 14 of the trial, if it is the opinion of the investigator that it is not appropriate for a subject to continue using Abilify MyCite, then the subject may be discontinued from trial participation but will be followed on oral atypical antipsychotic medication through the Month 6/ET visit.

If any subject discontinues the trial early, every effort should be made to complete the Month 6/ET evaluations (see [Table 3.7-1](#)) at that visit. All subjects (completers and early withdrawals) will be contacted to monitor for safety events via telephone or investigator visit at 1 month (\pm 3 days) after the Month 6/ET visit.

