5.7.2 Follow-up of Serious Adverse Events and Immediately Reportable Events

This trial requires that subjects be actively monitored for SAEs and IREs up to 1 month after the last dose of Abilify MyCite is administered.

Serious AEs and nonserious IREs that are identified or ongoing at the last scheduled contact must be recorded as such on the AE eCRF page. If updated information (eg, resolved status) on SAE or IRE status becomes available after a subject's last scheduled contact (up to the last in-clinic visit for the entire trial), this must be reported to the sponsor and recorded on the AE eCRF page, according to the appropriate reporting procedures. The investigator will follow SAEs until the events are resolved, stabilized, or the subject is lost to follow-up or has died. Resolution means that the subject has returned to the baseline state of health and stabilized means that the investigator does not expect any further improvement or worsening of the subject's condition. The investigator will continue to report any significant follow-up information to the sponsor up to the point the event has resolved or stabilized, or the subject is lost to follow-up or has died.

5.7.3 Follow-up and Reporting of Serious Adverse Events and Immediately Reportable Events Occurring after Last Scheduled Contact

Any new SAEs or IREs reported to the investigator, which occur after the last scheduled contact and are determined by the investigator to be reasonably associated with the use of Abilify MyCite, should be reported to the sponsor. This may include SAEs or IREs that are captured on follow-up telephone contact or at any other time point after the defined trial period. The investigator should follow SAEs or IREs identified after the defined trial period and continue to report any significant follow-up information to the sponsor until the events are resolved or stabilized, or the subject is lost to follow-up or has died.

Protocol 031-201-00301

6 Pharmacokinetic Analysis

Not applicable, no pharmacokinetic assessments will be performed in this trial.

7 Statistical Analysis

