The objective of this study is to compare inpatient psychiatric hospitalization rates (proportion of subjects with ≥ 1 inpatient psychiatric hospitalizations) between the retrospective period (Months 1 to 3) while subjects are on oral standard-of-care antipsychotic treatment and the prospective period (Months 1 to 3) after the subjects switch to Abilify MyCite.

3 Study Design

This is a phase 3b, open-label, prospective, clinical trial designed to assess the difference between inpatient psychiatric hospitalization rates in subjects on oral standard-of-care antipsychotic treatment(s) for a period of 6 months followed by a switch to Abilify MyCite for a period of 3 months (Months 1 to 3). At the Month 3 visit, the investigator should decide if subjects will continue on Abilify MyCite for an additional 3 months (Months 4 to 6) or switch to a standard-of-care treatment (eg, oral atypical antipsychotics or a long acting injectable [LAI]) for the duration of treatment.

This trial will include male and female subjects who are 18 to 65 years of age, inclusive, with a diagnosis of schizophrenia according to Diagnostic and Statistical Manual of Mental Disorders, Fifth Edition (DSM-5) criteria. Subjects must have had at least 1 inpatient psychiatric hospitalization within 4 years (48 months) and must have been prescribed oral antipsychotics for at least 6 months or longer prior to screening.

Subjects will enter a screening period (up to 45 days). If deemed eligible to participate, subjects will enter an open-label Abilify MyCite treatment prospective phase for up to 6 months. A schematic of the study design is provided in [Figure 3.1-1](#).

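### The SAP's TEAE definition starts at first MyCite but has no end, so adverse events that begin long after a subject has left MyCite are counted as treatment-emergent

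*SAP*

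**What the plan says.** SAP 8.1.1 has two limbs. The first is onset: "A treatment-emergent AE (TEAE) is defined as an AE which starts after start of study medication (MyCite". The second covers AEs continuing from baseline that are serious, drug-related, or lead to death or to stopping, interrupting or reducing study medication. Neither limb names a last-dose date, a number of days after it, or a switch. Protocol 7.6.1 lists TEAEs for summary without defining them.

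Leaving MyCite is a planned path. At Month 3 the investigator may continue MyCite "or switch to a standard-of-care treatment (eg, oral atypical antipsychotics or a long acting injectable [LAI]) for the duration of treatment" (Protocol 3.1). A subject judged unsuitable by Day 14 may be discontinued "but will be followed on oral atypical antipsychotic medication through the Month 6/ET visit" (Protocol 3.8.3.1).

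Safety observation continues after that. Protocol 3.7 says: "The Month 6/ET visit will serve as the final safety visit for subjects who complete the study on standard-of-care treatment". The Month 6/ET list in 3.7.1.3.5 includes "Monitor AEs, including device-related nonserious AEs" with no restriction to subjects on MyCite, although the accountability and dashboard items in the same list carry one. Protocol 5.2 times AE follow-up from the first dose, up to 7 months. The Safety Sample (SAP 5.1.1) keeps everyone with at least one dose.

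**The concern.** Safety and tolerability of MyCite is a secondary objective (Protocol 2.3.2). With an open-ended onset rule, an event that first appears months into a different antipsychotic falls under the same heading as an event on MyCite. The summaries then describe whatever subjects took during the prospective phase, and the mixing grows with the number who leave MyCite.

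The SAP draws the on/off distinction elsewhere. It separates concomitant medication into before, during and after study medication (8.2.3), defines emergent suicidality by reports made during treatment (8.1.6), and requires an on-treatment value for vital-sign abnormalities (Appendix 1). The AE definition has no counterpart.

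**Working it through.** The plan states no figure for this point, so there is none to reproduce. The check is day arithmetic on the plan's own calendar.

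**Inputs**
- A trial month is 28 days, and prospective Month 6 ends at MyCite start + 28×6 − 1, which is Day 168 (SAP 7.1.2).
- Last MyCite dose: Day 84 (28×3) for a Month 3 switcher; Day 14 for the earliest planned exit (Protocol 3.8.3.1).
- Illustrative window: last dose + 30 days. This is an assumption, chosen to match the 1-month SAE/IRE monitoring in Protocol 5.7.2.

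**Days on which a new AE still counts as a TEAE although MyCite has stopped**

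| | Month 3 switcher | Day 14 stopper, followed to Day 168 |
|---|---|---|
| Off-MyCite days | 168 − 84 = 84 (50%) | 168 − 14 = 154 (92%) |
| Window would close | 84 + 30 = Day 114 | 14 + 30 = Day 44 |
| Days beyond the window | 168 − 114 = 54 (32%) | 168 − 44 = 124 (74%) |

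**Share of person-time.** The documents give no switch rate. Among subjects followed to Day 168, if a share s switches at Month 3, the off-MyCite share is s × 84/168 and the share beyond last dose + 30 is s × 54/168.
- s = 25%: 12.5% and 8%
- s = 50%: 25% and 16%
- s = 75%: 37.5% and 24%

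**On the scale the tables use.** The TEAE tables report mainly the proportion of subjects with an event. Assume a constant hazard, equal on and off MyCite, and a 3-month incidence p. For Month 3 switchers, the incidence counted to Day 168 is 1 − (1 − p)^2, and to last dose + 30 it is 1 − (1 − p)^(114/84).
- p = 10%: 19.0% as written, 13.3% with the window
- p = 20%: 36.0% and 26.1%
- p = 30%: 51.0% and 38.4%

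The values of p are illustrations and do not come from the documents.

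**Which tables.** This depends on what is collected, and the documents differ.
- The Protocol synopsis and 3.1 name SAEs, device-related nonserious AEs, potential hepatotoxicity and pregnancies. On that reading the off-MyCite events are mainly SAEs, and the effect falls mainly on the serious and fatal summaries.
- Protocol 5.2 requires all reported AEs, serious and nonserious, to be recorded, and SAP 3.1 lists nonserious AEs without the device restriction. On that reading the overall, by-severity, ≥2% and ≥5% summaries are affected as well.

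**Is an end supplied elsewhere?** The interim analysis plan's restriction to data up to Month 3 applies only to the first interim. Protocol 5.7.2 says subjects are to be "actively monitored for SAEs and IREs up to 1 month after the last dose of Abilify MyCite is administered", which is a monitoring duty and does not limit what SAP 8.1.1 counts.

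**The case against.** The best defence is that the SAP rule agrees with Protocol 5.2, which counts AE follow-up from the first dose, so collection bounds the definition in practice. The summaries are descriptive and single-arm (Protocol 7.6). The drug-related and device-related tables filter by causality, and an open-ended rule can only add events; it cannot remove a MyCite event. All of this stands, and it limits the consequence. It does not supply an end to the rule, and a bound set by the end of collection still includes the whole off-MyCite period.

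A reader might infer three stronger things that the documents do not support.
- That the protocol already fixes a 1-month at-risk period which the SAP breaks. It does not: 5.7.2 concerns SAE/IRE monitoring, and the 30 days in 5.5 concern contraception and pregnancy reporting. Events after 30 days are therefore not misclassified against a stated standard.
- That the outputs have no split by treatment. In SAP Appendix 2, CT-8.1 carries *By Treatment* in its title and CT-8.6.1 and CT-8.6.2 refer to *Any Group*. The gap is that no rule assigns an AE to MyCite or to standard of care.
- That a nonserious injectable reaction in Months 4 to 6 is certain to appear as a MyCite TEAE. That holds only on the broader collection reading.

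The Day 14 figure is also an upper bound. Protocol 3.8.3.1 gives tracking of healthcare utilization as its reason for following subjects who stop early, and it asks for the ET evaluations when a subject leaves the trial. AE ascertainment over all 154 days is plausible but not assured.

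**Conclusion.** The concern holds as a gap in the definition. SAP 8.1.1 lets an AE count as a MyCite TEAE when it starts up to 84 days (Month 3 switcher) or up to 154 days (Day 14 stopper) after MyCite has stopped, and nothing else in the documents closes the window. These figures assume last doses at Day 84 and Day 14 and follow-up to Day 168.

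The number of events affected cannot be estimated, because neither switch rates nor event rates are given. The person-time shares show only how large the exposed period could be: they ignore dropout, and no planned output uses person-time. It would also go too far to say that the MyCite safety profile is unreadable. Causality-filtered tables remain, and the primary hospitalization test is untouched. The change should still be made, because the tables bearing on a secondary objective would otherwise mix treatments without saying so.

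**What to change.** In SAP 8.1.1:
1. Keep both limbs. Add an end to the onset limb only, tied to the last MyCite dose, for example last dose + 30 days in line with Protocol 5.7.2, or another window that the sponsor justifies. This is a counting rule for tables and changes nothing in subject care.
2. Put AEs with later onset in a separate post-MyCite table, by treatment taken at onset.
3. State the rule that assigns each AE to MyCite or standard of care, so that CT-8.1 and CT-8.6.1/8.6.2 can be produced as titled.
4. Reconcile the passages on which nonserious AEs are collected (Protocol synopsis and 3.1 against Protocol 5.2 and SAP 3.1), and the post-dose monitoring in 5.7.2 with AE assessment to Month 6/ET, so that the reach of the rule is known.

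The cost is a few sentences and some programming to link AE onset to last-dose and treatment-change dates. Treatment changes are already recorded in the eCRF. Late events leave the main TEAE tables but stay visible in their own table.
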